12.6. Other Endpoints

Analysis of these other endpoints will be conducted for exploratory purposes only. The efficacy endpoints listed below will be assessed based on the efficacy measurements conducted at the time points specified.

- Pain intensity scores
- The AUC of pain intensity scores

- Total opioid consumption in morphine equivalents
- Time to first postsurgical use of opioid medication.

12.7. Appropriateness of Measures

The endpoints selected for this study were based on well-established clinical measurements used in peer-reviewed studies.

13. STUDY PROCEDURES

A time and events schedule for study procedures is provided in Table 1. PK Sampling times are provided in Table 2.

13.1. Instructions for Conducting Procedures and Measures

All post-dose assessments will be timed from the end of study drug administration.

Day 1 is defined as the day on which study drug is administered. The beginning of surgery is defined as the time of the first incision. The end of surgery is defined as the time of the last suture/staple. Postsurgical is defined as after the end of surgery.

13.1.1. Pain Intensity Assessment

Pain intensity will be assessed using age-specific tools at screening; at 4, 8, 12, 24, 36, 48, 60, 72, and 96 hours after the end of study drug administration; immediately prior to each administration of postoperative opioid pain management medication till 96 hours; and at hospital discharge. Pain intensity scores will be collected using the following instruments:

- 11-point NRS-R for subjects aged 12 to less than 17 years (Appendix 1)
- CAS for subjects aged 6 to less than 12 years (Appendix 2)

13.1.2. Neurological Examination

A neurological assessment will be conducted during Part 1 only at the following time points: at screening; at 2, 4, 8, 12, 24, 36, 48, 60, 72, and 96 hours after the end of study drug administration; at hospital discharge; and on Day 30. The examination will include the subject's orientation. Additionally, subjects aged 6 years or older will be asked whether he or she is experiencing any numbress of the lips, the tongue, or around the mouth; hearing problems; or muscle twitching (see Appendix 3). If the subject answers "yes" to any of these questions, the event should be recorded as an AE and additional safety procedures should be conducted as appropriate (see Section 13.1.7).

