Part 1, Group 2, is a single-arm (EXPAREL 4 mg/kg), open-labeled, PK evaluation study in subjects aged 6 to less than 12 years undergoing spine or cardiac surgery. The sample size is a total of 15 subjects. Subjects will receive a single dose of EXPAREL 4 mg/kg (maximum 266 mg) intraoperatively at the end of surgery via local infiltration.

The total sample size for Part 1 is 45 subjects aged 6 to less than 17 years, with 30 subjects in Group 1 and 15 subjects in Group 2.

Part 2 (Safety) - Subjects aged 6 to less than 17 years

Part 2 is a multicenter, randomized, open-label, safety study in 45 subjects aged 6 to less than 17 years undergoing spine or cardiac surgeries. There will be two treatment groups: Group 1 will include subjects aged 12 to less than 17 years, while Group 2 will include subjects aged 6 to less than 12 years.

Part 2, Group 1, is an active-controlled, open-labeled, safety evaluation study in subjects aged 12 to less than 17 years undergoing spine surgery. The active comparator will be bupivacaine HCl. The sample size is a total of 30 subjects (15 subjects per treatment group). Subjects will be randomized 1:1 to receive either a single dose of EXPAREL 4 mg/kg (maximum 266 mg) or bupivacaine HCl 2 mg/kg (not exceeding a maximum bupivacaine HCl dose of 175 mg total) intraoperatively at the end of surgery via local infiltration.

Part 2, Group 2, is a single-arm (EXPAREL 4 mg/kg), open-labeled study in subjects aged 6 to less than 12 years undergoing spine or cardiac surgery. The sample size is a total of 15 subjects. Subjects will receive a single dose of EXPAREL 4 mg/kg (maximum 266 mg) intraoperatively at the end of surgery via local infiltration.

The total sample size for Part 2 is 45 subjects aged 6 to less than 17 years, with 30 subjects in Group 1 and 15 subjects in Group 2.

The overall safety assessments will include all 45 subjects from Part 1 and all 45 subjects from Part 2, with a total of 90 subjects.

Subjects will be screened within 30 days prior to study drug administration. During the screening visit, subjects will be assessed for past or present neurologic, cardiac, and general

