12.3. Safety Assessments

The following safety measurements will be conducted at the time points specified:

• Vital signs (temperature, resting heart rate, respiratory rate, oxygen saturation, and blood pressure) at screening; upon arrival in the post-anesthesia care unit (PACU); at 2, 4, 8, 12, 24, 36, 48, 60, 72, and 96 hours after the end of study drug administration; at hospital discharge; and on Day 30.

- Neurological assessment at screening; at 2, 4, 8, 12, 24, 36, 48, 60, 72, and 96 hours after the end of study drug administration; at hospital discharge; and on Day 30 (Part 1 only, Appendix 3).
- Clinical laboratory tests (hematology, chemistry, and urinalysis) at screening; at baseline (on Day 1 prior to surgery) and at 96 hours after the end of study drug administration (see Appendix 4).
- AEs from the time the ICF is signed/assent is obtained till Day 30.

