12.4. Safety Endpoints

The following safety endpoints will be assessed based on the safety measurements conducted at the specified time points:

- Change from baseline in vital signs (temperature, resting heart rate, respiratory rate, oxygen saturation, and blood pressure).
- Summary of neurological assessments (proportion of subjects who are oriented, and proportion of subjects who have any neurologic events). Note: Events identified during the neurologic assessment should be recorded as AEs.
- Change from baseline in clinical laboratory data.
- Incidence of TEAEs and SAEs till Day 30.

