13.2. Screening Procedures

- Explain study purpose and procedures.
- Obtain written informed consent/assent before performing any study-related procedures.
- Assess eligibility.
- Record relevant medical/surgical history, demographics, and baseline characteristics.
- Conduct urine pregnancy test for females of childbearing potential (Part 1 only).
- Perform physical examination.
- Perform neurological assessment (see Appendix 3; Part 1 only).
- Conduct clinical laboratory tests (hematology, chemistry, and urinalysis) (see Appendix 4).
- Conduct a urine drug screen and alcohol breath test at the investigator's discretion. Subjects with a positive result will be excluded from the study.
- Measure vital signs (temperature, resting heart rate, respiratory rate, oxygen saturation, and blood pressure) after subject has rested in a supine position.
- Conduct 12-lead ECG after subject has rested in a supine position.
- Record a pain intensity score using one of the following instruments:
 - 0 11-point NRS-R for subjects aged 12 to less than 17 years (Appendix 1)
 - CAS for subjects aged 6 to less than 12 years (Appendix 2)
- Record concomitant medications.
- Record AEs starting at the signing of the ICF/assent.

All subjects who are screened for enrollment, but do not meet eligibility criteria, who decline to participate, or whose parent or guardian decline the subject's participation, will be documented on a screening log with the reason for non-participation.

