13.5. Postoperative Assessments till 96 Hours

- Record age-specific pain intensity score at 4, 8, 12, 24, 36, 48, 60, 72, and 96 hours after the end of study drug administration; and immediately prior to each administration of postoperative opioid pain management medication. Pain assessments should be obtained before blood draws at the overlapping time points. If a subject is too anesthetized at the time of a scheduled pain intensity assessment, the assessment should be skipped. Pain intensity scores will be collected using the following instruments:
 - o 11-point NRS-R for subjects aged 12 to less than 17 years (Appendix 1)
 - CAS for subjects aged 6 to less than 12 years (Appendix 2)
- Perform neurological assessment at 2, 4, 8, 12, 24, 36, 48, 60, 72, and 96 hours after the end of study drug administration (see Appendix 3).

- Measure vital signs (temperature, resting heart rate, respiratory rate, oxygen saturation, and blood pressure) at 2, 4, 8, 12, 24, 36, 48, 60, 72, and 96 hours after the end of study drug administration.
- Collect blood sample for PK analysis at the procedure-specific time windows shown in Table 2; record the date and time each sample is collected.
- Collect blood sample for clinical laboratory testing (hematology, chemistry, and urinalysis) at 96 hours after the end of study drug administration (see Appendix 4).
- Record supplemental pain medications and concomitant medications used by the subject.
- Administer postoperative opioid pain management medication upon request, as needed. Record pain score prior to administration of such medication.
- Record date, time, and amount of all opioid pain management medication administered.
- Record other concomitant medications.
- Record AEs and any treatment(s) for the events.

Refer to Section 13.1.7 for additional procedures in the event a cardiac or neurological AE of special interest or SAE occurs.

Note: Subjects will be discharged from the hospital as indicated by their physician, and a nurse will perform follow-up visits at the subject's home to perform postsurgical assessments and collect PK samples till 96 hours.

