- Died on study (i.e., within 30 days of study drug administration)

Subjects will be counted once in each of the above categories except for maximum severity. Subjects will be counted only once at the highest severity reported. For example, if a subject has a mild and severe headache and a moderate rash, the subject will be counted under maximum severity of severe only.

Adverse event tables will present the data within each age group of the study. Incidence tables will be created for the following groups of TEAEs:

- All TEAEs by System Organ Class (SOC) and Preferred term (PT) sorted in descending order of frequency
- All TEAEs by relationship to study drug
- All TEAEs by severity
- All TEAEs of special interest
- All serious TEAEs

If there are no AEs to report on any of the above tables, the table should be created with the line 'no adverse events were reported' in the body of the table.

Adverse events will be considered related if the investigator assessment of relationship to study treatment is either 'possible', 'probable' or 'definite'. Adverse events will be considered unrelated if the

investigator assessment of relationship to study treatment is either 'unrelated', 'unlikely related'. All AE summaries based on related AEs will be produced based on the investigator assessment of relatedness.

Table 5 are the MedDRA terms for the adverse events of special interest according to the protocol. All AEs reported by investigators are based on this definition along with their clinical judgement.

		MedDRA 21.1 Dictionary Terms		
Group	Protocol term	Term Level	Term	
	Chest pain	Preferred term	Chest Pain	
Cardiac	Abnormal/irregular heart rate	Preferred term	Heart Rate Irregular	
	Shortness of breath requiring intervention	Preferred term	Dyspnoea	
	Seizure	Preferred term	Seizure	
	Altered mental status	Preferred term	Mental Status Changes	
	Altered sensorium	Preferred term	Depressed level of consciousness	
	Rigidity	Preferred term	Muscle Rigidity	
Neurologic	Dysarthria	Preferred term	Dysarthria	
	Tremors	Preferred term	Tremor	
	Tinnitus	Preferred term	Tinnitus	
	Visual disturbance	Preferred term	Visual Impairment	
	Dizziness*	Preferred term	Dizziness	
	Dizziness [#]	Preferred term	Dizziness	
	Hyperesthesia [#]	Preferred term	Hyperaesthesia	
Other	Muscular twitching [#]	Preferred term	Muscle Twitching	
	Tingling [#]	Preferred term	Paresthesia	
	Paresthesia [#]	Preferred term	Paresthesia	

Table 5. MedDRA Terms for AEs of Special Interest

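### Protocol sections disagree on whether neurological questioning stops after Part 1; if it does, the TEAE and AESI tables mix elicited and spontaneous reports with no display by Part

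*Protocol*

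**What the plan says.** Protocol 13.1.2 restricts the Appendix 3 questioning: "A neurological assessment will be conducted during Part 1 only at the following time points". The times are screening, ten points from 2 to 96 hours, hospital discharge and Day 30. Sections 12.3, 13.2, 13.6 and 13.8 also carry the restriction; 13.2, for example, reads "Perform neurological assessment (see Appendix 3; Part 1 only".

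Other places do not. Protocol 13.5, which covers the ten timed post-dose assessments, says "Perform neurological assessment at 2, 4, 8, 12, 24, 36, 48, 60, 72, and 96 hours after the end of study drug administration" and names no Part. The neurological row of Table 1 (reproduced in SAP Section 9) names none either, although the pregnancy-test and drug-and-alcohol rows are marked as Part 1. Appendix 3 and SAP 6.8.3 are also silent on Part.

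The answers feed the adverse event data. Protocol 12.4 notes: "Events identified during the neurologic assessment should be recorded as AEs". Section 13.1.2 and Appendix 3 say the same of any positive answer, and Appendix 3 adds disorientation.

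On reporting, Protocol 9.1 says the overall safety assessment "will include all 45 subjects from Part 1 and all 45 subjects from Part 2". SAP 6.8.4 says: "Adverse event tables will present the data within each age group of the study". SAP 6.1 adds treatment as the column in Group 1 and surgery type in Group 2. The TEAE shells (14.3-4.x) and AESI shells (14.3-6.x) show no Part in title, row or column.

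**The concern.** A child who is asked at scheduled times about numbness, taste, hearing, vision and twitching, and whose orientation is checked, will yield more recorded events than a child who must volunteer them. If the questioning is confined to Part 1, each pooled column combines two methods of ascertainment in equal planned shares, and the resulting percentage describes neither.

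Safety is the secondary objective and the protocol plans no hypothesis tests, so descriptive event rates are the main safety output. A low pooled rate of an elicitable symptom could be taken as reassurance from every child in the column when only half were asked. In Group 2 the columns are spine and cardiac surgery, and nothing in the plan fixes the mix of surgeries within each Part. A difference between those columns could therefore reflect how the children were assessed.

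**Working it through.** **1. Design counts.** The design table in Protocol 9.1 has six cells of 15. The total is 6 × 15 = 90, with EXPAREL 4 × 15 = 60 and bupivacaine HCl 2 × 15 = 30. This reproduces the protocol's 90, 60 and 30. Each Group 1 arm is 15 (Part 1) + 15 (Part 2) = 30. Group 2 is also 15 + 15 = 30, divided between spine and cardiac.

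**2. Exposure to questioning.** Section 13.1.2 lists 10 timed post-dose assessments plus discharge and Day 30, so up to 12 per child in Part 1. If its limit governs, Part 2 has none scheduled. If 13.5 and Table 1 govern, children in both Parts are questioned at the ten timed points and the mixing largely disappears. Steps 3 to 6 assume that the limit governs.

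**3. Dilution of the pooled rate.** Let p be the rate under questioning and f the fraction of those events that would be reported unprompted. The documents give neither, so both are assumptions.

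Pooled rate = (15p + 15fp)/30 = p(1+f)/2.

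| Assumed p | f = 0 | f = 0.5 | f = 1 |
|---|---|---|---|
| 10% | 5% | 7.5% | 10% |
| 20% | 10% | 15% | 20% |
| 40% | 20% | 30% | 40% |

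**4. Zero events.** The one-sided 95% upper limit for 0/n is 1 − 0.05^(1/n). For n = 30 it is 9.5%. For n = 15, the children actually asked, it is 18.1%.

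**5. Group 1 comparison.** Allocation is 1:1 within each Part, so both arms have the same planned share of questioned children. With a common f, assumed elicited rates of 40% and 20% become 20% and 10% at f = 0. The risk difference falls from 20 to 10 points and the ratio stays at 2. At f = 0.5 the rates are 30% and 15%, a difference of 15 points.

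**6. Group 2 columns.** Assume the same elicited rate of 20% for both surgeries, with 10 spine and 5 cardiac in Part 1 and 5 and 10 in Part 2.

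- f = 0: spine 10 × 0.20/15 = 13.3%; cardiac 5 × 0.20/15 = 6.7%.
- f = 0.5: spine (10 × 0.20 + 5 × 0.10)/15 = 16.7%; cardiac (5 × 0.20 + 10 × 0.10)/15 = 13.3%.

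At f = 0 the apparent gap depends on the assumed mix: 16% versus 4% for 12/3 then 3/12, and 10.7% versus 9.3% for 8/7 then 7/8.

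**7. Overlap with the AESI list.** Of the Appendix 3 items, vision problems match a term in SAP Table 5. Twitching does so only beyond 72 hours (Protocol 13.1.7). Hearing problems match only if coded as tinnitus, and disorientation only if coded as a mental status change. Perioral numbness and metallic taste have no row. The AESI tables are therefore exposed to part of the effect and the TEAE tables to all of it.

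**The case against.** The strongest reply is that the premise is not settled. A reader might infer from 13.1.2 that no Part 2 child is ever asked. The documents do not establish that, because 13.5 governs ten of the twelve post-dose assessments and has no limit, although the neighbouring 13.6 and 13.8 do. The SAP is mixed too: it drops the neurological rows from the combined-Parts baseline table for Group 1 but gives no such instruction for Group 2. This objection stands, and it makes the contradiction the first thing to resolve.

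Pooling is also inferred. Several other shells state that Parts 1 and 2 are combined; the TEAE and AESI shells do not. SAP Section 10 asks for a page break between Parts. SAP 6.9.2.1 plans time to first opioid by Part, yet its shell shows no Part either, so a silent title is not proof. Against this, Protocol 9.1 joins all 90 children for safety, SAP 6.8.4 names age group only, and no adverse event shell implements a split. Pooling is the likelier reading, but it is not stated.

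Third, SAP 6.8.3 already tabulates every Appendix 3 item after baseline, so the adverse event tables are not the only source for elicited symptoms. That is fair. It does not tell a reader of the TEAE and AESI tables that half of a column may not have been asked. By the SAP 6.1 default, the percentages in those neurological tables would also use the full group as denominator.

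A reader might also contrast limits for all 60 EXPAREL children with those for the 30 in Part 1. No planned adverse event table has a 60-child EXPAREL column, so the relevant comparison is 30 against 15.

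**Conclusion.** The point holds conditionally. The contradiction about which Parts receive the assessment is certain and must be reconciled. If the Part 1 limit governs and the tables pool as they appear to, the pooled rate of an elicitable symptom lies between 50% and 100% of the elicited rate, depending on an unknown f. A zero count then carries an upper limit of 9.5% where the questioned children alone support 18.1%.

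A reader might infer that the EXPAREL versus bupivacaine comparison is biased. The documents do not support this: 1:1 allocation within each Part balances ascertainment, and with a common f the ratio is unchanged while absolute rates and the risk difference shrink. Distortion between the Group 2 columns is a possibility that depends on a surgery mix the documents do not give. The AESI tables are affected less than the TEAE tables. All event rates, values of f and surgery mixes used above are assumptions.

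**What to change.** First, reconcile Protocol 12.3, 13.1.2, 13.2, 13.6 and 13.8 with 13.5, Table 1, Appendix 3 and SAP 6.8.3, so that all state the same Parts for the neurological assessment. Which schedule is right is for the sponsor to settle.

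If the answer is Part 1 only, add to SAP 6.8.4 a display by Part, with both Parts shown beside the pooled column, for the terms that Appendix 3 elicits and for neurological AESIs in Tables 14.3-4.2.x and 14.3-6.1.x. Footnote that ascertainment was by scheduled questioning in Part 1 and by spontaneous report in Part 2. Part 2 should stay in the display, because its stated purpose is safety. State in the same section that the pooled columns combine both Parts.

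The cost is SAP wording and one extra split in two table families. No new data are needed, since the disposition and population listings already carry Part. The drawback is small denominators: 15 per Group 1 arm in each Part, and fewer once Group 2 is divided by surgery type.

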13.1.3. Clinical Laboratory Tests

The scheduled clinical laboratory tests (hematology, chemistry, and urinalysis) will be conducted at screening; baseline (on Day 1 prior to surgery); and at 96 hours after the end of study drug administration (see Appendix 4). Clinical laboratory tests, as appropriate, may also be conducted if a subject experiences an AESI, or an SAE (see Section 13.1.7).

13.1.4. Vital Signs

The scheduled vital signs (temperature, resting heart rate, respiratory rate, oxygen saturation, and blood pressure) will be measured after the subject has rested in a supine position for at least 5 minutes at screening; upon arrival at the PACU; at 2, 4, 8, 12, 24, 36, 48, 60, 72, and 96 hours after the end of study drug administration; at hospital discharge; and on Day 30. Vital signs may also be measured if a subject experiences an AESI or an SAE (see Section 13.1.7). The subject will remain in a supine position during the assessment.

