	Screen Visit	D1 Preop	OR	15 min	30 min	1 h	2 h	4 h	8 h	12 h	24 h	36 h	48 h	60 h	72 h	96 h	Hosp Dis	D7 Call	D30 Visit
Time Window	Within 30 days			±5 min	±5 min	±15 min	±15 min	±15 min	±30 min	±1 h	±1 h	±2 h	±2 h	±2 h	±2 h	±4 h		±1 d	±3 d
Obtain signed informed consent/assent	Х																		
Assess/confirm eligibility	Х	Х	Х																
Record medical history and surgical history	Х	Х																	
Record demographics and baseline characteristics	Х																		
Urine pregnancy test (for females of childbearing potential; Part 1 only)	Х	Х																	
Urine drug screen and alcohol breath test at the investigator's discretion (Part 1 only).	Х	Х																	
Physical examination	Х																		Х
12-lead ECG ¹	X	2																	
Clinical laboratory tests (hematology, chemistry, urinalysis) ³	Х	Х														X			
Perform neurological assessment	Х						Х	Х	Х	Х	Х	Х	Х	Х	Х	Х	Х		Х
Measure and record vital signs ⁴	Х	Х					Х	Х	Х	Х	Х	Х	Х	Х	Х	Х	Х		Х
Record age-specific pain intensity score ⁵	Х							Х	Х	Х	Х	Х	Х	Х	Х	Х	Х		
Collect PK blood samples per time windows in Table 2				4 - ·							-				+				
Prepare study medication			Х																
Administer study medication; record dosage, volume, size of incision, and administration start and stop times			Х																
Record intraoperative opioids administered and doses			Х																
Record surgery start and stop times			Х																
Record times and doses of all pain management medication administered			•													• •			
Record date and time of discharge																	Х		

Table 1: Time and Events Schedule of Study Procedures

		Screen Visit	D1 Preop	OR	15 min										60 h			Hosp Dis	D7 Call	D30 Visit
	Time Window	Within 30 days			±5 min	±5 min	±15 min	±15 min	±15 min	±30 min	±1 h	±1 h	±2 h	±2 h	±2 h	±2 h	±4 h		±1 d	±3 d
	Document any unscheduled phone calls, unscheduled office visits, or ER visits related to pain after discharge																		Х	Х
Record prior and concomitant	nt medications ⁶	•													+					► X
Record AEs beginning at the signed ^{1,3,4,7}	Record AEs beginning at the time the ICF or assent is																			► X

Note: Postsurgical assessments will be conducted at the time points specified after the end of study drug administration.

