7.3. EXPAREL (bupivacaine liposome injectable suspension)

Bupivacaine is one of the longer-acting local anesthetics, but even so it has a limited duration of action after local administration, usually less than 8 hours. EXPAREL is a bupivacaine liposome injectable suspension. It consists of microscopic spherical, multivesicular liposomes (DepoFoam[®] drug delivery system), organized in a honeycomb-like structure comprising numerous non-concentric internal aqueous chambers containing a bupivacaine base at a concentration of 13.3 mg/mL. Each chamber is separated from adjacent chambers by lipid membranes. The lipids (phospholipids, cholesterol, and triglycerides) are naturally occurring or close analogs of endogenous lipids. Bupivacaine is slowly released from the DepoFoam particles by a complex mechanism involving reorganization of the barrier lipid membranes and subsequent diffusion of the drug over an extended period of time. EXPAREL has been noted in infiltration studies to have a bimodal curve (Apseloff 2013), with an initial peak occurring at approximately 0 to 2 hours and a second peak at approximately 24 to 48 hours (Hu 2013).

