6.8.1 Vital Signs

Vitals signs are resting heart rate (bpm), systolic blood pressure (mmHg), diastolic blood pressure (mmHg), temperature (°C), oxygen saturation (%), and respiratory rate (breaths/min). Vital signs will be summarized by treatment group (Group 1), and by surgery type (Group 2) at each assessment timepoint. Summaries will present both observed results by timepoint and change-from-baseline results. Baseline is defined as the last measurement on prior to the end of study drug administration . Baseline statistics will be presented at each assessment timepoint for those subjects reporting data at that timepoint.

Time windows will be derived for each post baseline visit using the time intervals for the study time windows detailed in Table 3.

Study Time	Time Interval for Study Time Window
Baseline	≥ 0 minutes prior to dose
Post-dose 2 hours	1.75 – 2.25 hours after end of study drug administration
Post-dose 4 hours	3.75 – 4.25 hours after end of study drug administration
Post-dose 8 hours	7.5 - 8.5 hours after end of study drug administration
Post-dose 12 hours	11 – 13 hours after end of study drug administration
Post-dose 24 hours	23 – 25 hours after end of study drug administration
Post-dose 36 hours	34 – 38 hours after end of study drug administration
Post-dose 48 hours	46 - 50 hours after end of study drug administration
Post-dose 60 hours	58 - 62 hours after end of study drug administration
Post-dose 72 hours	70 – 74 hours after end of study drug administration
Post-dose 96 hours	92 – 100 hours after end of study drug administration
Day 30	27 – 33 days after end of study drug administration

 Table 3
 Analysis Study Time Windows for Vital Signs Assessments

If there are multiple vital sign values for the same parameter prior to the end of study drug administration, the last value will be chosen for Baseline. If there are multiple vital sign values in a post-end of study drug administration window, the value closest to the target time point will be chosen for analysis. Unscheduled visits can be mapped to a study time only if the scheduled assessment for that time was not done and an unscheduled visit falls into the time interval for the visit window. Data from both scheduled and unscheduled visits will be listed.

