		EXPAREL	Bupivacaine HCl
		4 mg/kg	2 mg/kg
	Statistic	[N=xx]	[N=XX]
Number of Subjects on			
Rescue Medication (Opioid)	n (%)	xx (xx.x)	xx (xx.x)
No Rescue Medication (Censored)	n (%)	xx (xx.x)	xx (xx.x)
Time to First Rescue [1]			
Quartiles [2]			
First (25% rescued)	Estimate	XX.XX	XX.XX
	(95% CI)	(xx.xx,xx.xx)	(xx.xx,xx.xx)
Median (50% rescued)	Estimate	XX.XX	xx.xx
	(95% CI)	(xx.xx,xx.xx)	(xx.xx,xx.xx)
Third (75% rescued)	Estimate	XX.XX	XX.XX
	(95% CI)	(xx.xx,xx.xx)	(xx.xx, xx.xx)
Minimum	Observed	XX.XX	xx.xx
Maximum	Observed	xx.xx*	XX.XX

* indicates censored observation

CI = confidence interval

Subjects who are not administered an opioid rescue medication by 72 hours are censored at 72 hours after surgery or at the time of last follow-up, whichever is earliest. [1] Time 0 is defined as the time of the end of surgery.

[2] Estimates from Kaplan-Meier analysis.

Source: list SAS datasets used to create table

SAS X.Y

ddmmmyyyyThh:mm

program name

Table 14.2-4.1.3: Analysis of Time to First Postsurgical Opioid Medication Use (Group 2: 6 to < 12 years) - Safety Population

Note to programmer: Use preceding Table as template. Replace treatment columns by Spine Surgery and Cardiac Surgery for this table.

(Page X of Y)

Protocol: 402-C-319

Table 14.3-1.1.1: Summary of Vital Signs (Group 1: 12 to <17 years) - Safety Population

				EXPAREL 4 mg/kg	Bupivacaine HCl 2 mg/kg
Vital Sign	Timepoint	Value	Statistic	[N=xx]	[N=XX]
Resting Heart Rate (bpm)	Baseline	Actual	n	XX	XX
Resting heart Rate (bpm)	Dasettile	Actual	Mean	XX.X	XX.X
			SD	X.XX	X.XX
			Minimum	XX	XX
			Median	XX.X	XX.X
			Maximum	XX	XX
			manifiant		
	2 hours	Actual	n	XX	XX
			Mean	XX.X	XX.X
			SD	X.XX	X.XX
			Minimum	XX	XX
			Median	XX.X	XX.X
			Maximum	XX	XX
		Change from Baseline	n	XX	XX
			Mean	xx.x	xx.x
			SD	x.xx	x.xx
			Minimum	XX	XX
			Median	XX.X	XX.X
			Maximum	XX	XX

[1] Baseline (Day 1 prior to surgery) for subjects with data at the timepoin Source: list SAS datasets used to create table

ddmmmyyyyThh:mm

program name

SAS X.Y

Note to programmer: Vital signs are 'Resting Heart Rate (bpm)', 'Systolic Blood Pressure (mmHg)', 'Diastolic Blood Pressure (mmHg)', 'Temperature (°C)', 'Oxygen Saturation (%) and Respiratory rate (breaths/min)'. Timepoints to appear on this table are, in order of appearance, 2, 4, 8, 12, 24, 36, 48, 60, 72, and 96 hours, Hospital Discharge, and Day 30. Don't split timepoint across pages.

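### PACU-arrival vital signs are scheduled in three protocol places but missing from the schedule table, Section 13.5, the SAP windows and the output shells, so an early reading may be uncollected or only listed

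*Protocol*

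**What the plan says.** **Where the reading is scheduled.** The protocol synopsis, Section 12.3 and Section 13.1.4 all place vital signs "upon arrival at the PACU" (wording of 13.1.4) between the pre-dose and the 2-hour readings. Section 13.1.4 counts it among the scheduled measurements. Section 12.4 makes change from baseline in vital signs a safety endpoint, and safety is the secondary objective (Section 8.2).

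**Where it is missing.**
- Protocol Table 1: the row "Measure and record vital signs" is marked at screening, Day 1 preop, 2 to 96 h, hospital discharge and Day 30. There is no PACU column, and the row is blank at 15 min, 30 min and 1 h.
- Protocol Section 13.5: "Measure vital signs (temperature, resting heart rate, respiratory rate, oxygen saturation, and blood pressure) at 2, 4, 8, 12, 24" and so on to 96 h, with no PACU item.
- SAP Section 9 repeats the protocol's Table 1.
- SAP 6.8.1, Table 3: the row after Baseline is "1.75 – 2.25 hours after end of study drug administration".
- SAP Section 11, note to Table 14.3-1.1.1: "Timepoints to appear on this table are, in order of appearance, 2, 4, 8, 12, 24, 36, 48, 60, 72, and 96 hours", then hospital discharge and Day 30.
- SAP Listing 16.2-14.1.1: screening, baseline, 2 to 96 h, hospital discharge and Day 30.

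**The early peak.** Protocol Section 7.3 describes a bimodal curve in infiltration studies, "with an initial peak occurring at approximately 0 to 2 hours" and a second peak at about 24 to 48 h.

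**The concern.** The protocol contradicts itself about whether this reading is taken, and the SAP follows the version without it. Either a scheduled safety measurement is not collected, or it is collected and an early value has no place in the summaries of the endpoint it was meant to inform.

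The timing makes this more than a clerical mismatch. Part 1 draws PK samples at 15, 30 and 45 minutes and at 1 to 1.25 h to describe the early peak. The other scheduled safety assessments do not reach that period: neurological assessments start at 2 h, scheduled ECGs are pre-surgical, and the only post-dose laboratory tests are at 96 h. Apart from adverse event recording, PACU-arrival vital signs are the one scheduled safety assessment that can fall before the 2-hour window opens. Without them, the report would hold no summary of heart rate, blood pressure, respiration or oxygen saturation from most of the interval in which the protocol expects the first peak.

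**Working it through.** **1. Do the SAP windows follow the schedule?** Window = nominal time ± the tolerance in protocol Table 1.

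| Nominal (h) | Tolerance | Derived window (h) | SAP Table 3 (h) |
|---|---|---|---|
| 2 | 15 min | 1.75–2.25 | 1.75–2.25 |
| 4 | 15 min | 3.75–4.25 | 3.75–4.25 |
| 8 | 30 min | 7.5–8.5 | 7.5–8.5 |
| 12 | 1 h | 11–13 | 11–13 |
| 24 | 1 h | 23–25 | 23–25 |
| 36 | 2 h | 34–38 | 34–38 |
| 48 | 2 h | 46–50 | 46–50 |
| 60 | 2 h | 58–62 | 58–62 |
| 72 | 2 h | 70–74 | 70–74 |
| 96 | 4 h | 92–100 | 92–100 |

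All ten match exactly. SAP Table 3 agrees with protocol Table 1, so it carries over Table 1's omission of PACU arrival.

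**2. How much of the stated early-peak range is covered?** Range: 0 to 2 h (Section 7.3). The first post-dose window opens at 1.75 h.
- Covered: (2 − 1.75) / 2 = 0.125, or 12.5%.
- Not covered: 1.75 / 2 = 0.875, or 87.5%.

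**3. Do the early PK samples meet a vital signs window?** The first four sampling windows are 10–20, 25–35 and 40–50 min, and 1–1.25 h. The latest ends at 1.25 h, which is 0.5 h before the first vital signs window opens. None overlaps.

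**4. What happens to a collected PACU value?** SAP 6.8.1 assigns post-baseline values to the Table 3 windows. Where a window holds several values, it takes the one closest to the target time. Unscheduled values are mapped only if they fall in a window whose scheduled assessment was not done.
- Taken before 1.75 h: no window, no table row, listed only.
- Taken at 1.75 to 2.25 h: eligible for the 2 h row, but competes with the scheduled 2 h reading.
- Taken after 2.25 h and before 3.75 h: again no window.

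**5. Is the lack of a Table 3 window enough to exclude it?** Not by itself.

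| Time point | Table 3 window | Row in vital signs tables |
|---|---|---|
| Hospital discharge | No | Yes |
| PACU arrival | No | No |

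PACU arrival is the only post-dose vital signs time point scheduled in the protocol text that has neither.

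**6. How many children?** Planned total: 45 + 45 = approximately 90. The documents give no PACU arrival time relative to the end of study drug, so the number with a reading before 1.75 h can lie anywhere from 0 to about 90.

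**The case against.** The other side has five fair points.

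- **Collection is uncertain.** A reader might infer that the reading is taken in every child and then discarded. The documents do not show that. Table 1 and Section 13.5 leave it out, and the case report form against which the SAP was prepared is not among the documents. If that form follows Table 1, there is no scheduled PACU value to lose. This stands, and it makes the protocol inconsistency part of the point.
- **The 2-hour reading touches the peak range.** It would be too strong to call the PACU reading the only scheduled vital signs near the peak. The 2 h window covers the last quarter hour of an approximate range that comes from earlier infiltration studies, not from these children. This stands.
- **Arrival has no fixed clock time.** Study drug is given before wound closure, so arrival relative to the end of dosing will vary. A loss in all 90 children is not shown. This stands.
- **Listed data are still reported.** SAP 6.8.1 has scheduled and unscheduled values listed, and adverse events count from the start of study drug. So it would be wrong to infer that early values vanish or that a recognised event would be missed. The loss is from the summaries.
- **The analysis is descriptive.** No formal hypothesis testing is planned, and no comparison changes. This limits the consequence. It does not explain why a scheduled measurement of a named endpoint has no row.

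The SAP does say that vital signs are summarised by assessment time point, which could be read to include PACU arrival. The shell, however, lists its time points one by one and does not include it. SAP 6.11 declares only the added noncompartmental PK analysis as a departure from the protocol, so the omission is not presented as a decision.

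**Conclusion.** The point holds as a mismatch between documents with a limited but real effect on the safety summaries. The protocol schedules PACU-arrival vital signs in three places and leaves them out in two, and the SAP follows the omission throughout. Under the plan as written, the reading may not be collected. If it is collected before 1.75 h, it is listed only and enters no change-from-baseline summary.

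In size, 87.5% of the stated 0 to 2 h early-peak range lies before the first summarised post-dose window. The number of children affected is unknown and at most the approximately 90 planned. These figures take the protocol's approximate peak range at face value and read the table shell's time-point list as complete.

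The documents do not support saying that a value is lost in each of 90 children, that no scheduled reading reaches the peak range, or that early values are absent from the report. The change is worth making because it is nearly free and fills an early gap in a named safety endpoint.

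**What to change.** 1. **Reconcile the protocol.** Bring Table 1 and Section 13.5 into agreement with the synopsis and Sections 12.3 and 13.1.4 on whether vital signs are taken at PACU arrival. Which version stands is for the sponsor to decide.
2. **If the assessment is kept,** add a PACU-arrival time point to SAP Section 9 and Table 3, Tables 14.3-1.1.1 to 14.3-1.1.3, and Listings 16.2-14.1.1 and 16.2-14.1.2. Define it by visit label, as hospital discharge already is in the table shell, and show the actual time from end of study drug. A clock window of 0 to <1.75 h would not serve: it would miss later arrivals, could admit unscheduled or event-prompted readings under the PACU label, and has no target time for choosing among several values. Listing 16.2-23.1.1 already carries PACU admission date and time, so the timing can be checked.
3. **If the assessment is not kept,** state that in SAP 6.11.

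The cost is one extra row per table and listing and a schedule clarification. No sample size or method changes. If sites have been following Table 1, keeping the assessment also means taking a reading that the protocol text already schedules.
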